## Objectives and Endpoints

Objectives	Endpoints
Primary	
To determine if treatment with SZC, as adjunct to ACEi/ARB therapy (lisinopril or valsartan a ), is superior to placebo in slowing CKD progression, assessed as the reduction in participant's expected eGFR decline over time	Co-primary b 
 
Total slope: eGFR measurements starting at randomisation
 
Chronic slope: eGFR measurements starting at 12 weeks after randomisation
 

Secondary	
To determine if treatment with SZC, as adjunct to ACEi/ARB therapy (lisinopril or valsartan a ), is superior to placebo in reducing the incidence of the composite of kidney failure outcomes comprising: sustained $\geq 40\%$ decline in eGFR, onset of ESKD, and death from kidney failure	
 
Time from randomisation to the first occurrence of any component in the composite of                             
 
Sustained <math>\geq 40\%</math> decline in eGFR c
 
Onset of ESKD (kidney transplantation, maintenance dialysis, or sustained low eGFR) c
 
Death from kidney failure c
 
 
 

To determine if treatment with SZC, as adjunct to ACEi/ARB therapy (lisinopril or valsartan a ), is superior to placebo in reducing the incidence of lisinopril/valsartan dose decrease, in participants on lisinopril/valsartan at randomisation	
 
Time from randomisation to first lisinopril/valsartan dose decrease
 

To determine if treatment with SZC, as adjunct to ACEi/ARB therapy (lisinopril or valsartan a ), is superior to placebo in reducing albuminuria	
 
UACR measurements at scheduled visits after randomisation
 

To determine if treatment with SZC, as adjunct to ACEi/ARB therapy (lisinopril or valsartan a ), is superior to placebo in increasing serum bicarbonate levels	
 
Serum bicarbonate measurements at scheduled visits after randomisation
 

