## **9 STATISTICAL CONSIDERATIONS**

### **9.1 Statistical Hypotheses**

Statistical testing will be performed for all primary and secondary hypotheses. In all cases, the null hypothesis will be that of no difference between the treatment arms (SZC vs placebo). The family-wise Type I error rate will be controlled in the strong sense over the families of the primary and the secondary hypotheses.

Two co-primary hypotheses (corresponding to the evaluation of the difference in total and chronic eGFR slope, respectively) are defined in the study. Provided both of the primary hypotheses are rejected, the testing will proceed to the secondary hypotheses. A fixed sequence MTP will be applied to the family of all secondary hypotheses, with the order in the sequence following the order specified in [Table 4](#).

Both of the co-primary hypotheses will be tested at a two-sided significance level of 0.05. In accordance with the fixed sequence MTP, significance for a hypothesis corresponding to a secondary endpoint will be declared if the corresponding two-sided p-value is smaller than 0.05, provided that all other preceding hypotheses in the sequence have been rejected.

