### **9.2 Sample Size Determination**

Approximately 3000 participants will be enrolled (screened) to achieve approximately 1500 participants receiving at least one dose of SZC during the initiation phase, consequently leading to a target of 1360 participants randomly assigned to SZC or placebo.

Note that “enrolled” refers to a participant’s, or their legally acceptable representative’s, agreement to participate in the study following completion of the informed consent process.

The assumptions for variability of the eGFR measurements between and within participants used in the calculation below are taken from the DECLARE study (D1693C00001 [NCT01730534]): between-participant SD (ie, SD of the random slopes) of 2.6 and within-participant SD (ie, SD of the residuals) of 7.7. The difference in slopes in the 2 treatment arms is assumed to be 0.75, a magnitude that is deemed clinically relevant. For the purpose of sample size determination, it is also assumed that no acute effects are present, ie, that the decline in eGFR over time in both treatment arms is well-approximated by a single line with a particular slope.

Given this, and assuming a two-sided test of a difference in slopes based on a linear mixed model, with a two-sided significance level of 0.05, is performed, then approximately 1220 participants with complete eGFR data will provide a power of 91% for the evaluation of total slope. This is true provided the following time points for eGFR assessment, in terms of weeks since randomisation, are observed for each participant as a minimum: 0 (randomisation), 6, 12, 16, 20, 24, 46, 69, 92, 96, 100, and 104.

Under the same assumptions (ie, a difference in slopes of 0.75, no acute effect), the power for the chronic slope will be approximately 85%. The evaluation of the chronic slope is assumed to start at 12 weeks.

It is expected that approximately 20% of the eGFR data will be missing. As the eGFR data is correlated within participant, it is assumed that the data points available for a participant will provide information on the missed evaluations, and 20% of missed data would roughly correspond to approximately 10% of randomised participants with no eGFR data available. Hence, 1360 participants will be randomised in the maintenance phase.

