#### 9.4.2.1 Co-primary Endpoint(s)

##### Estimand

Population: Participants satisfying the inclusion and the exclusion criteria of the study and achieving normokalaemia after a 3-month run-in period, while on SZC treatment regimen, during which lisinopril/valsartan dose optimisation has been attempted.

Intervention: SZC and placebo, while receiving lisinopril/valsartan, as guided by the CSP.

Population-level summary: Difference in population-level eGFR slopes between SZC and placebo.

Intercurrent events: In general, the intercurrent events that lead to a potential change in the measurements profile, but for which post-intercurrent event data are available (eg, treatment discontinuation, introduction of eGFR altering concomitant therapy), will be ignored, and all eGFR data obtained, both pre and post the intercurrent event will be used in the primary analysis. This would correspond to a treatment policy approach as per ICH E9 (R1) and align with the intention-to-treat principle. The exception to this rule will be the events for which it could be argued that, after experiencing these, a participant ceases to belong to the population of interest, namely onset of ESKD as defined in Section 8.1.2. For such an event, any data collected post event occurrence will be excluded from the analysis of the primary objective.

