The main strategy for handling the intercurrent events in the analysis of the primary objective will be that of treatment policy. That is, the intercurrent events that lead to a potential change in the measurements profile, but for which post-intercurrent event data are available (e.g. treatment discontinuation, introduction of eGFR altering concomitant therapy), will be ignored in the analysis, and all data obtained, both pre and post the intercurrent event, will be included as planned. In the table below, the approach for handling intercurrent events described above is referred to as “main strategy”. The exception to this rule will be the events for which it could be argued that, after experiencing these, a participant ceases to belong to the population of interest. For such an event, any data collected post event occurrence will be excluded from the main analyses. Onset of ESKD is the only type of event currently identified in this category.

In addition to the main analyses, a number of supplementary analyses of the primary and secondary endpoints, utilizing a hypothetical intercurrent event strategy, will be carried out. In this case, data from after the intercurrent events that lead to a potential change in the measurements profile will not be used in the analysis. Instead, a hypothetical scenario that the intercurrent event did not have occur will be considered. For example, for the intercurrent event of long-term potassium lowering treatment and a hypothetical strategy, it will correspond to a hypothetical situation where such treatment is not available to participants. An equivalent situation will apply to the remaining hypothetical intercurrent events.

Missing data: If not otherwise specified, no imputation of missing data will be performed. Rather, missing data will be handled indirectly through e.g., application of models for longitudinal data, such as regressions with random effects, and survival analysis approaches. The same applies for missing covariate data used in the sub-group analyses: no imputation will be performed.

One exception to this rule will be the eGFR measurements obtained as re-tests, if, due to operational reasons such as unavailability of kits, the planned eGFR samples could not be taken at a scheduled visit (see Section 4.2.1). Such measurements may be used in the eGFR-based analyses.

Covariates: For each of the model-based analyses detailed below, the following variables are included as covariates in the model:

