4.2.2.1 Main analysis

Derivations:

Time to the first occurrence of the components as listed in Table 2, namely sustained $\geq 40\%$ decline in eGFR, onset of ESKD or death from kidney failure, will be derived as the difference between the date of the occurrence and the randomization date, plus one day.

Explicitly, for the different components as listed in CSP Section 8.1.2:

Sustained percent decline in eGFR, is defined as percent decline in eGFR of $\geq 40\%$ from the point of randomisation over at least 4 weeks, as evidenced by 2 consecutive central

laboratory measurements taken at least 4 weeks apart. The start date of the event is the date of the first central laboratory measurement.

Onset of ESKD, is defined as meeting any of the three of the following conditions:

- Kidney transplantation, the date of which is collected directly in the eCRF in a dedicated renal event module.
- Maintenance dialysis, defined as dialysis performed for at least 4 weeks. The date of the start of the dialysis will be used as onset of ESKD date.
- Sustained low eGFR, defined as eGFR < 15 mL/min/1.73 m² over at least 4 weeks, as confirmed by 2 consecutive, non-missing central laboratory measurements < 15 mL/min/1.73 m² taken at least 4 weeks apart. The date of the first such measurement will be used as the date of onset of ESKD.

Death from kidney failure is defined directly by the investigator in the eCRF, as an AE, with the AE date being considered as the date that the event has occurred.

Analysis:

The evaluation of the secondary objective of reducing the incidence of composite outcome of $\geq 40\%$ sustained decline in eGFR, onset of ESKD, and death from kidney failure, will be performed by means of a Cox regression.

The patients will be censored at the end of the maintenance phase, or at the time they leave the study prematurely for any reason (e.g., the date of ICF withdrawal, or the date of last contact in case of a patient lost to follow-up), if such an event occurs. The null hypothesis of no difference between the treatment arms will be tested by considering the hazard ratio (HR) estimate corresponding to treatment. As for other analyses, the estimates of the treatment effect (i.e., hazard ratio between the two treatment arms) alongside the corresponding 95% CI and a p-value, will also be provided.

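### Both co-primary slope models drop eGFR measured after a sustained eGFR below 15, so the outcome itself decides which values are analysed; the effect is small and conservative, and the repair is cheap

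*Protocol*

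**What the plan says.** The endpoint table describes the component as "Onset of ESKD (kidney transplantation, maintenance dialysis, or sustained low eGFR". That row belongs to the secondary composite and contains no deletion rule. The rule is in the estimand text.

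- Protocol 9.4.2.1 adopts a treatment-policy approach, with one exception, for ESKD under the Section 8.1.2 definition: "For such an event, any data collected post event occurrence will be excluded from the analysis of the primary objective". The reason given is that such a participant can be regarded as no longer part of the target population. SAP 4.2 repeats the exception: "For such an event, any data collected post event occurrence will be excluded from the main analyses".
- Protocol 8.1.2 defines sustained low eGFR as below 15 on two consecutive central measurements at least 4 weeks apart, with the re-sample at an unscheduled visit. It gives no onset date for this component.
- The date appears only in the derivation of the secondary endpoint, SAP 4.2.2.1: "The date of the first such measurement will be used as the date of onset of ESKD".
- SAP 4.2.1.1 fits the slope models to eGFR from scheduled visits, now only up to visit 17 (week 69). SAP 3.3.3 keeps unscheduled data out of visit-based analyses.
- SAP 4.2 leaves missing data mainly to the longitudinal models.

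**The concern.** Dialysis and transplantation make creatinine-based eGFR uninterpretable as native kidney function. A measured value of 12 on native kidneys is different: it is the outcome the slope is meant to describe. Under the rule, once a first value falls below 15, the next central value decides whether later scheduled values stay. If it is below 15 they go; if it is 15 or above they stay. That deciding value is not in the model. It is either deleted itself (when a scheduled visit supplies it) or was unscheduled and never eligible. A likelihood-based mixed model protects against missingness that depends on values it sees, and this deletion depends on one it does not.

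The values lost come from participants with the lowest eGFR, and more often from the arm that declines faster. Both slopes should look flatter than the data collected would show, and a real difference should be pulled towards zero. Success requires both co-primary tests, and the chronic slope has the lower planned power.

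Nothing retained would reveal the effect. The protocol's shared parameter model for ESKD or death, and its imputation below 15 after dialysis or transplantation, are absent from SAP 4.2.1.2 to 4.2.1.3.

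**Working it through.** **Inputs from Protocol 9.1 and 9.2.** "Both of the co-primary hypotheses will be tested at a two-sided significance level of 0.05". "The difference in slopes in the 2 treatment arms is assumed to be 0.75" (read as mL/min/1.73 m² per year). Slope SD is 2.6 and residual SD 7.7. There are 610 participants per arm, with visits at weeks 0, 6, 12, 16, 20, 24, 46, 69, 92, 96, 100 and 104.

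**Step 1: the plan's own figures.** With complete data, the SD of one participant's slope is √(2.6² + 7.7²/Sxx), where Sxx is the sum of squared deviations of the visit times in years. SE = SD × √(2/610), and power = Φ(0.75/SE − 1.96).

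- Total slope: Sxx = 6.71, SD = 3.95, SE = 0.226, power 91.3%. The protocol says "approximately 1220 participants with complete eGFR data will provide a power of 91% for the evaluation of total slope".
- Chronic slope (weeks 12 to 104): Sxx = 4.86, SD = 4.36, SE = 0.249, power 85.3%. The protocol says "the power for the chronic slope will be approximately 85"%.
- Randomised number: 1220/0.90 = 1356, against 1360 planned.

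The stated figures reproduce, so the same model can be used to test the rule.

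**Step 2: simulation of the rule.** Each participant's eGFR was linear in time, with a screening value of 25 to 59, slope SD 2.6 and a true benefit of 0.75. The first of two consecutive values below 15 was kept and every later scheduled value deleted. The mixed model was fitted to the same data with and without the deletion (200,000 participants, 5 repeats). These inputs are assumptions, not in the documents:

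- mean eGFR 35 or 40 before screening selection (SD 8 or 9);
- placebo slope −3 to −5 per year;
- residual SD 4.0 as an alternative to 7.7;
- an unscheduled re-sample at 5 weeks;
- central eGFR at every visit to week 69;
- no dialysis or death.

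Shift in the estimated difference, total / chronic:

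| Mean eGFR, placebo slope, residual SD | Events by week 104, placebo v SZC | Week 104, unscheduled confirmation | Week 69, unscheduled confirmation | Week 69, confirmation at next scheduled visit |
|---|---|---|---|---|
| 40, −3, 7.7 | 3.5% v 2.7% | −0.013 / −0.015 | −0.003 / −0.002 | −0.008 / −0.009 |
| 40, −5, 7.7 | 7.0% v 5.4% | −0.022 / −0.025 | −0.003 / −0.003 | −0.011 / −0.013 |
| 35, −4, 7.7 | 9.3% v 7.4% | −0.029 / −0.033 | −0.004 / −0.005 | −0.018 / −0.022 |
| 40, −4, 4.0 | 2.6% v 1.7% | −0.007 / −0.008 | −0.0005 / −0.0007 | −0.002 / −0.0025 |
| 35, −5, 4.0 | 7.9% v 5.6% | −0.014 / −0.017 | −0.0015 / −0.0017 | −0.006 / −0.007 |

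The largest shift over 104 weeks came from the third row with confirmation at the next scheduled visit: −0.034 / −0.038. Over 104 weeks the placebo slope was 0.02 to 0.19 per year too flat.

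**Step 3: relative size.**

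- 104 weeks: 0.007/0.75 = 1% to 0.038/0.75 = 5%.
- Week 69, confirmation at the next scheduled visit: 0.002/0.75 = 0.3% to 0.022/0.75 = 3%.
- Week 69, unscheduled confirmation: 0.0005/0.75 = 0.1% to 0.005/0.75 = 0.7%. One run with visit-specific residual SDs gave up to 0.008 (1%), with a simulation error of 0.004.

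**Step 4: power over 104 weeks, SE unchanged.**

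- Second row, whose event rate matches the roughly 7% ESKD the protocol expects. Total: (0.75 − 0.022)/0.226 − 1.96 = 1.26, power 90%. Chronic: (0.75 − 0.025)/0.249 − 1.96 = 0.95, power 83%.
- Largest shift: (0.75 − 0.034)/0.226 − 1.96 = 1.21, power 89%; (0.75 − 0.038)/0.249 − 1.96 = 0.90, power about 81%.

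A separate simulation at residual SD 7.7 put the loss at 2 to 5 points.

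**Step 5: no true effect.** The shift in the difference was 0.0001 over 104 weeks and at most 0.0005 at week 69, both within simulation error.

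**The case against.** The exclusion is deliberate and stated. On the sponsor's estimand the slope ends at ESKD, so a shift appears only against a different target, the slope over all measured native-kidney eGFR. That stands, and it is why the point is put relative to that target. But the stated reason fits dialysis and transplantation better than a low measured value, and the rest of the estimand follows treatment policy.

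A reader might infer four stronger claims that the documents do not support.

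- *The confirming value is always the one deleted.* Protocol 8.1.2 asks for it at an unscheduled visit, so it is normally outside the model anyway. It is deleted only when a scheduled visit supplies it, as can happen at weeks 12 to 24 and 92 to 104, where visits are 4 weeks apart. Otherwise only later scheduled values are lost.
- *The 104-week losses apply to the analysis now planned.* The study closed early and the slope models stop at week 69, where the shift is much smaller.
- *A false positive is at risk.* The shift is towards zero and vanishes without a treatment effect.
- *No rule changes treatment at these eGFR levels.* Protocol 7.1.1 gives sustained eGFR below 20 as an example of when lisinopril/valsartan is discontinued, and SAP 4.2 recognises that dose changes may shift eGFR acutely. Later values may therefore reflect that stop, which the simulation's straight-line decline ignores. Follow-up does continue: Protocol 7.1.1.1 keeps participants who stop one intervention in the study for all visits.

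**Conclusion.** The concern holds as a modest one. Deletion after a sustained eGFR below 15 depends on the outcome, and the mixed model's missing-at-random handling does not cover it. A true 0.75 difference shrinks by about 1 to 5% over 104 weeks, or roughly 1 to 5 power points at residual SD 7.7 and less at smaller SDs. In the current week-69 analysis it shrinks by about 0 to 3%, and generally well under 1% with unscheduled confirmation. The direction is conservative. The sizes rest on the assumed baseline eGFR, placebo slope and undisturbed linear decline. The documents do not give the number randomised at early closure, so power for the week-69 analysis cannot be computed. This is a cheap improvement, not a threat to the validity of a positive result.

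**What to change.** In Protocol 9.4.2.1 and SAP 4.2, limit the exclusion to eGFR taken after the start of maintenance dialysis or after kidney transplantation. State that scheduled eGFR measured after a sustained value below 15 stays in both slope models under the treatment-policy strategy. Leave the event date in the kidney composite unchanged.

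Starting the cut after the confirming sample is only a partial repair. When that sample is unscheduled, it is still outside the model and the later scheduled values are still lost, so that version should not be called unbiased.

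The cost is a sentence in each document and a small programming change, using data already collected. The downside is a small change to the stated estimand, since retained values may partly reflect a lisinopril/valsartan stop. Keeping the present exclusion as a sensitivity analysis would show whether that matters.

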## Overall Design

This is a Phase 3, international, randomised withdrawal, double-blind, parallel-group, placebo-controlled study, to evaluate the effect of SZC as adjunct to RAASi therapy (lisinopril or valsartan) in slowing CKD progression in participants with CKD and hyperkalaemia or at risk of hyperkalaemia.

Specifically, the study will include participants with hyperkalaemia (S-K > 5.0 to  $\leq$  6.5 mmol/L by central laboratory) who are on adequate or limited RAASi therapy due to hyperkalaemia, and participants with normokalaemia (S-K  $\geq$  3.5 to  $\leq$  5.0 mmol/L by central laboratory) who are on limited RAASi therapy due to high risk of hyperkalaemia. High risk of hyperkalaemia is defined as (1) participants with a previous medical history or record of hyperkalaemia within the prior 24 months who are on limited RAASi therapy despite indication in CKD; (2) participants in whom RAASi therapy is indicated in CKD but are on limited RAASi therapy and have S-K  $\geq$  4.7 to  $\leq$  5.0 mmol/L; and (3) participants in whom RAASi therapy has been discontinued or reduced to suboptimal doses because of hyperkalaemia.

The study will be conducted at up to 250 study sites in up to 16 countries.

**Screening Period (Up to 13 days)**

During the screening period, after signed informed consent is obtained, data required for determination of eligibility for the study will be collected and inclusion/exclusion criteria evaluated. Participants who fulfil the study eligibility criteria may proceed to the initiation phase. Participants who do not fulfil the study eligibility criteria are screen failures and may be rescreened once.

**Initiation Phase (Up to 72 hours)**

No changes will be made to the ACEi/ARB therapy during the initiation phase. The initial dosing of SZC will be based on the participant's S-K as measured by local laboratory on the same day as, or within 24 hours prior to, Day 1 (Visit 2); the S-K results MUST be available before any other Visit 2 procedures/assessments are performed.

**Participants who are hyperkalaemic (S-K > 5.0 to  $\leq$  6.5 mmol/L [local laboratory])** will receive 10 g SZC three times daily (TID) starting on Day 1 (Visit 2). S-K will be measured by local laboratory at 48 hours (Day 3; Visit 3b) and subsequently at 72 hours (Day 4; Visit 3c) if normokalaemia (S-K  $\geq$  3.5 to  $\leq$  5.0 mmol/L) has not been previously achieved.

In case the S-K result is not available for up to 24 hours after sample collection, the participant will be notified by phone as soon as possible after the S-K results are available, and the following instructions should be followed for SZC:

- Day 3 (Visit 3b): if the 48-hour S-K result is not available, the participant will take SZC 10 g TID for one additional day.
- Day 4 (Visit 3c): if the 48-hour S-K is  $> 5$  to  $\leq 6.5$  mmol/L and the 72-hour S-K is not available, the participant will take SZC 10 g once daily (QD) for one day.

If normokalaemia is achieved after 48 or 72 hours of treatment with SZC, the participant will proceed to the run-in phase, during which SZC dosing will be initiated at 10 g QD.

Participants who do not achieve normokalaemia after 72 hours of treatment will undergo a follow-up visit at 7 ( $\pm 2$ ) days after the participant's last dose and exit the study.

**Participants who are normokalaemic (S-K  $\geq$  3.5 to  $\leq$  5.0 mmol/L [local laboratory])** will receive SZC 5 g QD starting on Day 1 (Visit 2) for 48 hours. S-K will be measured by local laboratory at 48 hours (Day 3; Visit 3b). In case the S-K result is not available for up to 24 hours after sample collection, the participant will continue with a third day of SZC 5 g QD and will be notified by phone as soon as possible after the 48-hour S-K results are available.

If normokalaemia is maintained after 48 hours of treatment with SZC, the participant will proceed to the run-in phase, continuing to receive 5 g QD. Participants who do not maintain normokalaemia after 48 hours of treatment will undergo a follow-up visit at 7 ( $\pm 2$ ) days after

the participant's last dose and exit the study. NOTE: Visit 3c is not applicable for participants who are normokalaemic at Visit 2.

